1 STUDY BACKGROUND

1.1 STUDY OBJECTIVES

The main research question is whether the current "Behavioral Test for the Development of medications for Alcohol Dependence" (TEMA) can demonstrate that the administration of acamprosate or ionized Calcium (Ca^{2+} = finished drug Calcium-Verla®) reduces the willingness to work for alcohol in a laboratory experiment following a 15- to 20-day period of alcohol abstinence.

The willingness to work for alcohol is determined by the cumulative number of work trials in the "constant attention task" (CAT). The change in this willingness due to the administration of acamprosate, Ca²⁺, or placebo is expressed as the difference in the cumulative number of work trials in the CAT per test day between Visit 2 (without medication) and Visit 5 (after administration of scamprosate, Ca²⁺ or placebo).

The hypothesis to be tested is that the administration of acamprosate compared to placebo or the administration of calcium ions compared to placebo, leads to a significant reduction in the willingness to work in the laboratory experiment to obtain alcohol.

Based on literature reports that form the basis of the sample size calculation, a relevant change is considered to be a reduction in blood alcohol concentration (BAC) of at least 0.1 per mille in one of the active treatment groups between Visit 2 and Visit 5 compared to the placebo group. In terms of the primary endpoint, this corresponds to a reduction in the cumulative number of work trials for alcohol infusions by 60.

Secondary objectives

The study aims to investigate whether:

- 1. the administration of acamprosate or calcium ions (Ca^{2+} = ready-to-use drug Calcium-Verla®) compared to placebo leads to altered subjective perception of alcohol effects
- 2. the efficacy of acamprosate or calcium ions can be predicted by basal levels or the change over time in measures of body calcium reserves reflecting a possible calcium deficiency
- 3. the administration of acamprosate or calcium ions reduces alcohol craving in daily life
- 4. the frequency of reported alcohol consumption during the imposed abstinence period differs between the treatment groups and how this affects the willingness to work for alcohol after the imposed abstinence period
- 5. participation in the study promotes the motivation to change drinking habits or alters drinking habits or the utilization of addiction treatment services
- 6. the activity of secreted sphingomyelinase is suitable as a biomarker for alcohol consumption and prediction of medication effects
- 7. safety issues occur during the use of the investigational medicinal products

- 8. the administration of acamprosate or ionized calcium (Ca²⁺ = ready-to-use drug Calcium-Verla[®]) lowers threshold at which participants decide it is no longer worthwhile to work for an additional alcohol reward ("break point").
- 9. the administration of acamprosate or ionized calcium (Ca²⁺ = finished medicinal product Calcium-Verla®) reduces the maximum and mean blood alcohol concentration (BAC) in an alcohol self-administration experiment.
- 10. the administration of acamprosate or ionized calcium (Ca^{2+} = ready-to-use drug Calcium-Verla®) reduces the work for saline infusions as an alternative reinforcer.
- 11. the aforementioned points (1 to 3 and 8 to 10) differ in the first and second half of the experiment.
- 12. the acamprosate level in the group of subjects treated with acamprosate influences the primary outcome of the aforementioned points

1.2 STUDY DESIGN

This is a monocentric study in a placebo-controlled, randomized design with three treatment groups. The administration of the investigational drugs is conducted in a double-blind manner with placebo, acamprosate, or calcium carbonate.

The comparison will be made between the calcium group and the placebo group, as well as between the acamprosate group and the placebo group.

Self-infusion of the NIMP (alcohol / saline solution) will be conducted openly regarding the preparation and single-blind regarding the dosage during visits alcohol self-administration visits V2 and V5.

2 ANALYSIS POPULATIONS

2.1 DEFINITIONS

The intent-to-treat population (ITT) to be analyzed comprises all randomized subjects who were administered the investigational product (excluding the placebo lead-in medication and alcohol) at least once. The statistical analysis of this population determines whether the results are statistically significant or statistically non-significant.

2.2 SERIOUS PROTOCOL VIOLATORS

The per-protocol population (PP) will also be analyzed. This population includes all subjects from the intent-to-treat population who attended visits V5 and V6. Subjects with serious protocol violations will be excluded from the per-protocol analysis. For the analysis of the primary endpoint, these violations include, for example:

- Participants in the acamprosate group with no detectable acamprosate levels in their blood (V5), and
- participants in the calcium group where the temporal profile of body calcium reserve parameters indicates non-compliance with the investigational drug (e.g., a significant drop in calcium levels or an increase in parathyroid hormone).

2.3 FURTHER ANALYSIS

Separate analyses of the ITT and PP populations will be conducted for all subjects who received at least one alcohol infusion during visit 5 (2nd alcohol self-administration). Subjects who only requested saline infusions at visit 5 will not be included in these analyses.

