4.2 PRIMARY ENDPOINT

The primary outcome measure is the difference in the cumulative number of work trials for alcohol in the "constant attention task" (CAT) [CATALC] between the first (V2) and second (V5) self-administration experiment, compared between the acamprosate vs. placebo and calcium vs. placebo treated groups [MED].

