6.3 EXPOSURE TO THERAPY AND COMPLIANCE

Randomization will be stratified according to the two criteria:

- a) Severity of addiction characteristics up to the time of V4
 - "High" if there is at least a moderate alcohol use disorder according to DSM-5, i.e., the presence of at least 4 of the 11 criteria, or if significant physical alcohol withdrawal symptoms were reported anamnestically or observed by study physicians (CIWA at V3 or V4 > 6 points).
 - "Low" if there is only a mild alcohol use disorder according to DSM-5, i.e., the presence of no more than 3 of the 11 criteria, and physical withdrawal symptoms were neither reported anamnestically nor observed by physicians..

b) Answer to the question at time V4 as to whether patients want to reduce their alcohol consumption ("yes" or "no")

This stratification aims to ensure that the distribution of these two characteristics does not differ between the three treatment arms before the start of treatment.

It is hypothesized that acamprosate will have a more pronounced effect the more severe the addiction-related pathological changes in the reward system are. This aspect is captured by the composite factor "Severity of Addiction Characteristics" (criterion a).

Since the overwhelming majority of acamprosate studies in humans only included patients who wanted to reduce or stop their alcohol consumption, the clinical efficacy insights of acamprosate are limited to this group. On the other hand, it seems

inappropriate to make the desire for reduction a prerequisite for participation, as based on animal experiments and the observations of Mason et al. (2006), acamprosate reduces alcohol consumption even when there is no explicit desire for change, especially under the specific conditions of prior enforced abstinence.

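### Section 2.3 repeats the ITT and PP analyses only in subjects who took alcohol at V5, a post-randomisation condition driven by the outcome; the confirmatory test is unaffected

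*SAP*

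**What the plan says.** Section 2.3 of the SAP states: "Separate analyses of the ITT and PP populations will be conducted for all subjects who received at least one alcohol infusion during visit 5". It then adds: "Subjects who only requested saline infusions at visit 5 will not be included in these analyses". It names no endpoint, test, rationale or limit on interpretation.

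The main question in section 1.1 is whether treatment "reduces the willingness to work for alcohol in a laboratory experiment following a 15- to 20-day period of alcohol abstinence". The primary endpoint in section 4.2 is the "difference in the cumulative number of work trials for alcohol" between V2 and V5. Section 1.1 places V2 before medication and V5 after it: "the difference in the cumulative number of work trials in the CAT per test day between Visit 2 (without medication) and Visit 5". Section 6.3 stratifies randomisation on "Severity of addiction characteristics up to the time of V4" and on an answer given at V4, so that the distribution of these features "does not differ between the three treatment arms before the start of treatment".

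Section 2.1 lets the ITT analysis alone decide statistical significance, and section 6.1 makes ITT primary.

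**The concern.** Whether a subject receives alcohol at V5 is decided after randomisation, on treatment, and by the same behaviour that the primary endpoint measures. A subject who takes none at V5 shows the fullest response to the question in section 1.1, and section 2.3 removes that subject.

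If the section is read as repeating the between-arm efficacy comparison, two things follow. First, the quantity changes: any effect that runs through taking no alcohol is left out by construction. Second, if treatment alters who takes alcohol, the remaining subjects are no longer the groups that were randomised, and the balance sought by the stratification may be lost.

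What is at stake is the reading of a supportive result. A subset contrast that differs from ITT could be taken as failing to support it when the difference comes from the selection.

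**Working it through.** **Timing.** V2 is before medication (section 1.1). Randomisation uses V4 information (section 6.3), so it comes no earlier than V4. V5 is after medication. The V5 condition is therefore post-randomisation; a V2 condition would not be.

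**Link to the endpoint.** The endpoint is the change in work for alcohol from V2 to V5, and alcohol infusions are the reward for that work. The condition is not exactly V5 work above zero, because a subject can start work and stop before the first reward. The illustrations below use V5 work above zero as an approximation.

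**Inputs.** The SAP supplies one usable figure, the relevant effect: "this corresponds to a reduction in the cumulative number of work trials for alcohol infusions by 60". It gives no subset figure to reproduce, and no SD, work level or no-alcohol share. Everything else here is assumed. Contrasts are active minus placebo in V5 minus V2 work, with the ITT contrast fixed at -60.

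**1. Purely graded effect.** V2 and V5 work are bivariate normal, censored at 0, with mean 300, 400 or 500, SD 150, 225 or 300, and correlation 0.5, 0.7 or 0.85 (27 settings, 1,000,000 simulated subjects). A common downward shift at V5 is solved to give ITT = -60.
- No alcohol at V5: 0 to 16% on placebo, 0 to 23% on active.
- Subset contrast: about -56 to -67. It is at least as large as ITT in about a third of the settings.
- Effect in subjects who would take alcohol under either treatment: -60 to -74. Lost balance therefore moves the contrast towards zero by 0 to 17 trials.
- Subset defined instead by V2 work above zero: -60 to -68.

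**2. Part or all of the effect through random abstaining.** Assume that those who take alcohol work 400 trials on average, that 5% of placebo take none at random, and that a share f of the effect comes from extra random abstainers. Each extra abstainer costs 400 trials, so the extra share is 60f/400 = 0.15f. The rest, 60(1 - f), is spread over the 0.95 - 0.15f who still take alcohol:

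subset contrast = -60(1 - f) / (0.95 - 0.15f)

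| f | calculation | subset contrast |
|---|---|---|
| 0% | -60/0.95 | -63.2 |
| 25% | -45/0.9125 | -49.3 |
| 50% | -30/0.875 | -34.3 |
| 75% | -15/0.8375 | -17.9 |
| 100% | 0/0.80 | 0 |

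The subset equals -60 where 1 - f = 0.95 - 0.15f, that is f = 0.05/0.85, about 6%.

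**3. Whole effect through the lightest V5 workers stopping.** Work is gamma with mean M = 200, 300 or 600 at both visits, SD 0.6M, V2-V5 correlation 0.6, and no placebo abstainers. Let p be the share of the active arm whose combined V5 work averages 60 trials per subject in that arm. Those left have V5 mean (M - 60)/(1 - p). In this model their V2 mean is raised by 0.6 of the V5 gain, so

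subset contrast = 0.4 x [(M - 60)/(1 - p) - M]

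| M | p | V5 mean of those left | subset contrast |
|---|---|---|---|
| 200 | 53.1% | about 298 | +39 |
| 300 | 41.2% | about 408 | +43 |
| 600 | 26.3% | about 732 | +53 |

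Simulation with 1,000,000 per arm gave +39, +43 and +52. The same mechanism under a log-normal model with mean 400 gave +12 to +45.

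**The case against.** No decision rests on section 2.3. It is headed as further analysis, and sections 2.1 and 6.1 give the decision to ITT. This stands and sets the severity.

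Section 2.3 names no endpoint. Section 4.3.1 plans subjective alcohol effects, and section 6.5.1 analyses them with alcohol-infusion endpoints as covariates. Restricting those analyses to subjects who received alcohol is natural. This stands in part: nothing limits section 2.3 to those endpoints, so the efficacy reading is open but not certain.

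The large distortions come from imposed shares of 25% or more of the effect through taking no alcohol. In the graded model that share is only 0.1 to 4.3%, and the largest shrinkage against ITT is under 4 trials. This stands as well: the SAP says nothing about the share.

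A reader might infer more than the document supports:
- That the confirmatory result or the type I error is compromised. The ITT set carries no V5 alcohol condition.
- That the subset contrast must shrink whenever the drug works. The graded model gives a contrast as large as ITT or larger in about a third of settings, and the random-abstaining formula does so for f below about 6%.
- That the figures bound the bias. Different assumed mechanisms give different signs.
- That the per-protocol exclusions in section 2.2 share this fault. That list is illustrative, PP is secondary, and an unstated general caveat about PP is not an error.

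**Conclusion.** The point holds as a minor one about a supportive analysis. As written, section 2.3 allows a between-arm efficacy contrast in a set chosen after randomisation through the V5 half of the primary endpoint. Such a contrast does not estimate the treatment effect on willingness to work for alcohol.

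How far it would depart from ITT cannot be derived from the SAP. The assumed cases run from little departure to a reversed sign, depending on how much of the effect acts through taking no alcohol and on who abstains. If treatment does not change who takes alcohol, the subset keeps its balance.

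**What to change.** In section 2.3:

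1. Report the number and proportion with no alcohol infusion at V5, by arm, as an outcome.
2. If an efficacy analysis in drinkers is wanted, define the subset by at least one alcohol infusion at V2, which precedes medication and randomisation.
3. Keep the V5 subset only for describing subjective alcohol effects, and label any between-arm contrast in it as descriptive and not protected by randomisation.

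The cost is a few lines of SAP text and one extra proportion per arm. The drawback is that a V2-defined subset includes subjects with no alcohol at V5, so it cannot replace the V5 subset for subjective effects. In the graded illustration it also largely repeats ITT.

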2.4 SAFETY PARAMETERS

The safety parameters will be analyzed using the Safety Analysis Set. This population comprises all subjects who have at least started the administration of an investigational product (including placebo lead-in). The subjects are assigned to the treatment group according to treatment they actually received (analysis "as treated").

4 ANALYSES VARIABLES

4.1 DEMOGRAPHICS AND BASELINE CHARACTERISTICS

The following data will be recorded: Age in years [AGE], gender [SEX], education level [SCHOOL], training / qualification / degree [QUALI], existing partnership (yes/no) [FAMSTAT; 0=no; 1=yes], living alone (yes/no) [LIFE; 0=no; 1=yes], net household income [INCOME].

Laboratory parameters: Complete blood count [HB, HCT, WBC, PLT, RBC, MCH, MCHC, MCV], ALAT [ALT], ASAT [AST], lipase [LIPA], Crea [CREA], eGFR [eGFROTH], Quick [QUICK], Calcium [CAL], S-ASM [SASM])

Clinical Interviews:

- Diagnostic short Interview for Mental Disorders (Mini-DIPS) [DIPSRES; DIPSSEQ; DIPSTERM]
- Medical assessment of the dependence criteria [SU1 to SU11; 0=no, 1=yes] for alcohol according to DSM-5 and alcohol dependence according to ICD-10 [SUNY = dependence according to ICD 10; 0=no, 1=yes]
- Lifetime Drinking History, including total drinking duration [LtDHDUR], duration of heavy drinking [LtDHHEA], duration of abstinence [LtDHABS], total amount of alcohol consumed [LtDHTOT], average daily alcohol consumption [LtDHDAI]

Family history using the Family History Assessment Module and Individual Assessment Module (FHAM-IAM) for parents, grandparents and siblings, resulting in a family history [FMHRES; 1=pos; 2=neg] and family density score [FMHFDS].

Questionnaires used:

- Fagerström test for nicotine dependence (FTND) [FTND], including smoking status [SMOKERNY; 1=yes, 0=no]
- Alcohol Use Disorders Identification Test (AUDIT) [AUDIT_QS]
- Alcohol Dependence Scale (ADS) [ADS]
- Barrat Impulsiveness Scale (BIS) [BIS]
- Substance use risk profile scale (SURPS), including Hopelessness [SUPRSH], Anxiety Sensitivity [SUPRSA], Impulsivity [SURPSI], Sensetion Seeking [SURPSS]

Additional laboratory and clinical examinations

Vital parameters (pulse [PULSE], blood pressure [SYSBP; DIABP]), height [HEIGHT], weight [WEIGHT]

4.2 PRIMARY ENDPOINT

The primary outcome measure is the difference in the cumulative number of work trials for alcohol in the "constant attention task" (CAT) [CATALC] between the first (V2) and second (V5) self-administration experiment, compared between the acamprosate vs. placebo and calcium vs. placebo treated groups [MED].

4.3 SECONDARY ENDPOINTS

4.3.1 Endpoints related to efficacy

- 1. Additional parameters of alcohol self-administration:
 - Difference between visit 2 and visit 5 of the "break points" [BPALC] in the "progressive work" task for alcohol. The "break point" corresponds to the performance requirement at which subjects decide it is no longer worth working for another reward (alcohol) and thus stop working on the CAT before reaching the next reward.
 - Difference in maximum blood alcohol concentration (BAC) [BACMAX] and b) mean BAC [BACMEAN] during alcohol self-administration between visits 2 and 5
 - Difference between visit 2 and 5 in the cumulative number of work cycles for saline [CATWAT] in the "constant attention task"
 - Analysis of the primary and the above-mentioned secondary parameters of alcohol self-administration with separate consideration of only the first and second half of the experiment respectively. For this purpose, the cumulative number of work cycles for alcohol and saline in the CAT is recorded every 30 seconds during an experiment [CATALC_T0 to CATALC_T300].
- 2. The subjective alcohol effects will be measured using visual analog scales ("quizzer") before, during and after the experiment at visits 2 and 5 in order to

compare alcohol-induced changes between the 3 treatment arms. The raw values and the "slopes" (increases) between consecutive measurement points will be used for analysis.

The following measures will be collected at 4 points in time (before the experiment, twice during the experiment, once after the experiment):

- a) stimulation [VAS1T1, VAS1T2, VAS1T3, VAS1T4],
- b) Sedation [VAS2T1, VAS2T2, VAS2T3, VAS2T4]
- c) Negative Feelings [VAS3T1, VAS3T2, VAS3T3, VAS3T4]
- d) Desire for more alcohol [VAS4T1; VAS4T2; VAS4T3; VAS4T4]
- e) Positive feelings [VAS5T1; VAS5T2; VAS5T3; VAS5T4]
- f) Drinks [VAS6T1; VAS6T2; VAS6T3; VAS6T4]
- g) Feeling drunk [VAS7T1, VAS7T2; VAS7T3; VAS7T4]
- h) Thirsty [VAS8T1; VAS8T2; VAS8T3; VAS8T4]
- 3. Parameters of body calcium reserves will be measured: The blood levels of total calcium [CAL], phosphate [PHOS], magnesium [MG], albumin [ALB], parathyroid hormone [PAHO], 25-hydroxyvitamin D [VITD] at visit 2 and visit 5. Baseline values and the difference in values between V2 and V5 will be considered to examine their relationship to the primary endpoint value in the three treatment arms.
- 4. Alcohol craving in daily life will be measured using the "Obsessive Compulsive Drinking Scale" (OCDS, from obsessive [OCDSO], compulsive [OCDSK] and total score [OCDST]) before both self-administration experiments (V2 and V5) to compare treatment-related changes between the 3 treatment arms
- 5. Violations of the imposed abstinence are recorded as the proportion (%) of days with alcohol consumption detected (by TLFB) [VABST] to compare them between the three treatment arms and to investigate their influence on the primary endpoint.
- 6. Motivation to change drinking habits. The "Readiness to change" questionnaire is used to determine which of the three stages of change in drinking habits the participants are currently assigned to. Subscores of the Pre-Contemplation [RTCP], Contemplation [RTCC] and Action [RTCA] will be anlyzed. Differences between the stage of change before the study (screening), after completion of the study procedures (visit 6) and after completion of the brief intervention (telephone follow-up) will be considered independently of the treatment arm. The number of participants for whom the readiness to change increases, remains the same and decreases will be described.
- 7. Drinking habits will be assessedusing the Timeline follow-back interview (TLFB) at screening (or re-screening), at visits 1, 3 and 6 and at the telephone follow-up. Changes in drinking habits as a result of study participation will be recorded by comparing the drinking amounts during the 45 days prior to the start of the study (measured at the screening or re-screening) with those after the end of the study (telephone follow-up interview). The following points will be examined in each of the 3 treatment arms:
 - a) the percentage of drinking days [TFbITT],
 - b) the average amount drunk per drinking day [TFbIAVE],
 - c) the percentage of days with heavy alcohol consumption (over 60 g for men and 48 g for women = "binge days") [TFbIBT], and
 - d) the average amount of alcohol on these binge days [TFbITM]

- 8. Determine whether participants have ever received addiction treatment services [SSBNY] (e.g., addiction-specific counseling/treatment by an addiction counseling center or general practitioner or psychologist or psychiatric specialist or hospital) in comparison before study participation (for screening) and afterwards (visit 6 and telephone follow-up interview)
- 9. Baseline values and change in secreted acid sphingomyelinase activity (at screening [SASM] and at both self-administration experiments, V2 and V5 [SASM1 and SASM2, respectively]) in serum in relation to drinking behavior (TLFB values), primary and secondary endpoints of alcohol self-administration, and medication effects on these outcomes
- 10. The acamprosate levels [APS] (for the second self-administration experiment, visit 5) in relation to primary and secondary endpoints of alcohol self-administration in the acamprosate group.

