6.4 CONFIRMATORY ANALYSIS

Testing the two primary hypotheses

- H1: The administration of acamprosate compared to placebo leads to a significant reduction in the willingness to perform work in the laboratory experiment to obtain alcohol
- H2: The administration of calcium ions compared to placebo leads to a significant reduction in the willingness to perform work in the laboratory experiment to obtain alcohol infusions

Will be conducted using t-tests if the data is normally distributed. The test for normal distribution will be assessed using the Shapiro Wilk test and a graphical inspection of the distribution in the histogram. If the data is not normally distributed, Mann-Whitney tests will be used. The significance level is 0.025, as two null hypotheses are tested in the confirmatory analysis.

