6.5 SECONDARY ANALYSES

6.5.1 Efficacy

All parameters listed below will be examined descriptively in a first step and only analyzed using exploratory statistical methods if notable differences or discrepancies are observed. The aim of exploratory data analysis is to generate hypotheses as a basis for future research projects.

Secondary endpoints related to alcohol self-administration will include:

a. Difference between visit 2 and visit 5 of the "break points" in the "progressive work" scheme for working for alcohol. The "break point" represents the performance threshold at which participants decide it is no longer worth working for another reward (alcohol) and thus stop the CAT before reaching the next reward.

The comparison of the difference in break points between Visit 2 and Visit 5 among the three groups will be conducted descriptively using frequency tables, median, range, maximum, minimum, and appropriate graphical representation.

b. Difference in maximum and mean blood alcohol concentration (BAC) achieved during alcohol self-administration between visits 2 and 5.

This parameter will be analyzed using analyses of variance (ANOVAs).

c. Difference in the cumulative number of work trials for saline solution in the "constant attention task" between visit 2 and visit 5:"

The differences in the three groups will be compared using ANOVA.

d. Investigation of the primary and the above-mentioned secondary parameters of alcohol self-administration, considering only the first and second halves of the experiment. For this purpose, the cumulative number of work trials for alcohol and saline in the CAT will be recorded every 30 seconds during an experiment.

The analyses will be conducted according to the primary and the relevant secondary parameters of alcohol self-administration.

In addition, the following secondary questions will be investigated:

1. does the administration of acamprosate or calcium ions compared to placebo lead to altered subjective perception of alcohol effects?

The subjective perception of alcohol effects will be measured using visual analog scales ("quizzer") before, during and after the experiment at visits 2 and 5 in order to compare their alcohol-induced changes between the 3 treatment arms. The values and the "slopes" (changes) between two measurement points will be analyzed.

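### Secondary objective 11 asks whether drug effects differ between session halves, but the SAP analyses each half separately and plans no between-half contrast for the self-administration parameters

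*SAP*

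**What the plan says.** SAP section 1.1, secondary objective 11, asks whether "the aforementioned points (1 to 3 and 8 to 10) differ in the first and second half of the experiment". The points it refers to concern what acamprosate or calcium does to subjective alcohol effects, craving, break point, BAC and saline work, and whether calcium measures predict efficacy.

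Section 4.3.1, item 1, turns this into an analysis of the primary and secondary self-administration parameters "with separate consideration of only the first and second half of the experiment respectively". It adds that "the cumulative number of work cycles for alcohol and saline in the CAT is recorded every 30 seconds during an experiment".

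Section 6.5.1, item d, repeats the scope ("considering only the first and second halves of the experiment") and gives the method in one sentence: "The analyses will be conducted according to the primary and the relevant secondary parameters of alcohol self-administration". Each half therefore inherits the whole-session methods:

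- alcohol work trials: t-test or Mann-Whitney test (section 6.4)
- BAC and saline work: ANOVA (6.5.1, items b and c)
- break points: descriptive summaries (6.5.1, item a)

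The opening of 6.5.1 governs all of this. Parameters are described first and "only analyzed using exploratory statistical methods if notable differences or discrepancies are observed", with hypothesis generation as the stated aim.

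**The concern.** A question about whether a treatment effect differs between two periods is a question about an interaction. Separate analyses of the two periods do not estimate it. One half can reach significance and the other miss it when the effect is the same in both. Conversely, both halves can be significant when the effects really differ.

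At stake is a statement that acamprosate or calcium works early in the session but not late, or the reverse. Such a statement could shape hypotheses for later trials. The SAP provides no analysis of work trials, BAC, break points or saline work that would check it.

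The problem is present even for measures that split cleanly by half, such as alcohol work trials.

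**Working it through.** **Text check.** For each element that an answer to objective 11 would need:

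| Element | In the SAP? |
|---|---|
| Question about a difference between halves | Yes, section 1.1, objective 11 |
| Results within each half | Yes, 4.3.1 item 1 and 6.5.1 item d |
| Variable for the between-half difference | No |
| Half as a factor, or an arm-by-half term, for the self-administration parameters | No |
| Rule for concluding that the halves differ | No |
| Data from which a contrast could be built | Yes, 30-second alcohol and saline counts |

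**How often discordance arises by chance.** The SAP gives no half-wise power, standard deviation or correlation, so it has no figure to reproduce. What follows is an illustration on stated assumptions.

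Inputs:

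- Level 0.025 per comparison, from section 6.4 ("The significance level is 0.025, as two null hypotheses are tested in the confirmatory analysis"). Sidedness is not stated; two-sided is assumed.
- One test statistic per half, bivariate normal with unit variance and the same true mean (equal effect in standard-error units). Assumed.
- Power P per half of 50% or 80%. Assumed.
- Correlation rho between the two statistics of 0.3 to 0.7. Assumed.

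Formula: P(exactly one half significant) = 2 × [P − P(both significant)].

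At P = 0.5 there is a closed form, because the mean then sits on the critical value and the far tail is negligible: P(both) = 1/4 + arcsin(rho)/(2π).

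- rho 0.3: P(both) = 0.250 + 0.0485 = 0.2985, so 2 × (0.5 − 0.2985) = 0.403
- rho 0.5: P(both) = 0.250 + 0.0833 = 0.3333, so 2 × (0.5 − 0.3333) = 0.333
- rho 0.7: P(both) = 0.250 + 0.1234 = 0.3734, so 2 × (0.5 − 0.3734) = 0.253

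The other rows come from the bivariate normal distribution function:

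| True effect in each half | rho 0 | 0.3 | 0.5 | 0.7 | 0.9 |
|---|---|---|---|---|---|
| Equal, 50% power | 0.500 | 0.403 | 0.333 | 0.253 | 0.144 |
| Equal, 80% power | 0.320 | 0.268 | 0.226 | 0.174 | 0.100 |
| None | 0.049 | 0.047 | 0.043 | 0.036 | 0.022 |

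Check of one cell: with no effect and rho 0, 2 × (0.025 − 0.025²) = 0.049.

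The figures are per active-versus-placebo comparison and per endpoint. At level 0.05 the rows with an effect are unchanged to three decimals, and the no-effect row runs from 0.095 (rho 0) to 0.041 (rho 0.9).

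**What a direct contrast does.** When the effect on the count scale is equal in both halves, a test of the between-half contrast at level 0.025 declares a difference in 2.5% of trials per comparison.

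**Scale.** The illustration takes equality in standard-error units, while a contrast of counts tests equality in raw counts. The two coincide only if the half-wise standard errors are equal. Suppose the drug lowers work at V5 by the same proportion p in both halves, and the expected placebo levels are m1 and m2. The raw effects are p·m1 and p·m2, and their difference p·(m2 − m1) is not zero unless m1 = m2. Under a progressive work scheme the levels may well differ between halves.

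**The case against.** The strongest reply is that the SAP never says it will compare two p-values. Item d sits under a descriptive-first rule, half-wise tests may never be run, break points are only ever summarised, and the purpose is to generate hypotheses. This stands in part. A reader might infer that discordant halves will be reported as a difference; no sentence in the SAP sets such a rule, so the text supports only that they could be. The gate does not remove the gap, however. Notable is left undefined, and half-wise results remain the only material the SAP offers on this question for the self-administration parameters.

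A reader might also infer that nothing in the SAP looks within the session. That goes too far. The visual analog scores are taken four times per session, their slopes between measurement points are analysed, and section 6.5.1 gives them a repeated measures ANOVA. It names no half contrast, though, and does not cover work trials, BAC, break points or saline work.

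Objective 11 could also be read more loosely, as asking only whether the arms differ within each half. Sections 4.3.1 and 6.5.1 fit that reading. If it is what the sponsor meant, the objective should be reworded and no between-half claim made.

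Finally, the 17% to 40% range applies only if a real effect exists with the assumed power. With no effect the figure is far smaller, as the table shows. Both cases belong in the assessment.

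**Conclusion.** The mismatch is real: on its natural reading the objective asks for a between-half difference, and the stated method for the self-administration parameters does not estimate one. Chance discordance could be taken for a difference. The risk is 25% to 40% at 50% power per half and 17% to 27% at 80% power, given equal effects in standard-error units and a correlation of 0.3 to 0.7. It is about 2% to 5% at level 0.025 when there is no effect in either half. Power, correlation and sidedness are assumptions, since the SAP states none of them.

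The consequence is limited to one exploratory secondary objective. The primary endpoint, its test and its significance level are untouched. The change is worth making because it is cheap and gives the stated question an analysis that addresses it.

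**What to change.** In section 6.5.1, item d, for alcohol and saline work trials:

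1. Split each session's cumulative counts at the midpoint: first half is the midpoint count minus the starting count; second half is the final count minus the midpoint count.
2. For each participant derive D = (V2-V5 difference in the second half) − (V2-V5 difference in the first half).
3. Compare D for acamprosate versus placebo and for calcium versus placebo, and report each estimate with a confidence interval, labelled exploratory. This is equivalent to the arm-by-half term in a model with half as a within-subject factor.
4. State that any claim that effects differ between halves rests on this contrast, not on separate half-wise p-values.
5. Note that D is on the raw-count scale, so an equal proportional effect can give a non-zero contrast when work levels differ between halves. Show the half-wise levels by arm and visit alongside.
6. Keep the half-wise results as descriptive estimates.

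In section 1.1, restrict objective 11 to measures that have a value in each half. Craving (point 3) does not: the OCDS is completed before each experiment. The calcium measures in point 2 are taken per visit, not per half.

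The cost is a few lines of SAP text and one derived variable from counts already recorded. No new data are needed and the confirmatory analysis is unchanged.
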